## 11.1 TOXICITIES/SIDE EFFECTS

The dose delay and reduction instructions provided in Tables 11A and 11B are intended to serve as guidelines to allow ongoing treatment for patients experiencing clinical benefit without signs or symptoms of progression while ensuring patient safety. Patients may temporarily suspend dosing of LY3023414 for up to 14 days if they experience toxicity that is considered related to LY3023414 and requires that a dose be held. Patients who miss ≥ 14 consecutive days of scheduled LY3023414 treatment because of LY3023414 related AEs will be discontinued from the study. LY3023414 dosing delay beyond 2 weeks and up to 28 days may be permissible, if AEs are not considered to be primarily related to LY3023414 and the investigator deems continuation to have clinical benefit for the patient. Exceptions may be made after discussion with the approval by the Principal Investigator. Patients may suspend dosing of study drug for radiation therapy or surgery that is considered by the treating physicians to be of clinical benefit for the patient. After completion of the intervention, patients may restart the study drug as long as all criteria for dosing are met and there is no evidence of disease progression (unless approved by PI and sponsor as noted previously).

Dose modifications for LY3023414 for select AEs, should follow the guidance provided in Table 11A, and required dose reductions should follow the dose levels outlined in Table 11B. No dose re-escalation will be allowed.

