**Table 11B: LY3023414 Dose Reduction Schedule**

Starting Dose	200mg twice daily
Dose Level -1	150mg twice daily
Dose Level -2	100mg twice daily
Dose Level -3	Discontinue

It is expected that patients with nausea, emesis, diarrhea, or constipation will receive appropriate medical management without dose modification. However, patients with

persistent ( $\geq 24$  hours) Grade  $\geq 3$  toxicity in spite of optimal medical management require reduction of one dose level and delay in subsequent therapy for a maximum of 2 weeks until recovered to Grade 1.

Other non-hematologic toxicities with an impact on organ function of Grade  $\geq 2$  require reduction of one dose level and delay in subsequent therapy for a maximum of 28 days until recovered to Grade 1, or pre-therapy baseline

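### The hold and discontinuation rules in Section 11 conflict for drug-related toxicity: day 14 is both permitted and terminal, and a 28-day limit is not reconciled with the 14-day one

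*Combined protocol and SAP*

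**What the plan says.** Section 11.1 (Toxicities/Side effects) gives four statements in sequence:

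- Permission: "Patients may temporarily suspend dosing of LY3023414 for up to 14 days if they experience toxicity that is considered related to LY3023414".
- Discontinuation: "Patients who miss ≥ 14 consecutive days of scheduled LY3023414 treatment because of LY3023414 related AEs will be discontinued from the study".
- Extension: a delay of more than two weeks and up to 28 days may be acceptable "if AEs are not considered to be primarily related to LY3023414" and the investigator sees clinical benefit in continuing.
- Exception: "Exceptions may be made after discussion with the approval by the Principal Investigator". No scope or limit is given.

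The section then sends the reader to Table 11A for dose modification and says that "required dose reductions should follow the dose levels outlined in Table 11B". Two further limits follow Table 11B:

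- For persistent gastrointestinal toxicity of Grade 3 or higher, the plan sets a one-level reduction and a "delay in subsequent therapy for a maximum of 2 weeks until recovered to Grade 1".
- For organ-function toxicity, a second rule covers "Other non-hematologic toxicities with an impact on organ function of Grade" 2 or higher. Such events "require reduction of one dose level and delay in subsequent therapy for a maximum of 28 days until recovered to Grade 1"; a return to the level seen before treatment also counts as recovery.

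Neither of these two limits carries a condition on attribution. Table 11A, whose title confines it to drug-related events, states no maximum hold. Section 13.1 lists a delay of more than 28 consecutive days among reasons that may lead to discontinuation. It does not separate related from unrelated events and has no 14-day item.

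**The concern.** These rules decide whether a patient with drug toxicity is treated again or taken off study, so each case should lead to one action. Three do not:

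1. A related hold of exactly 14 days.
2. A related organ-function toxicity held for 15 to 28 days.
3. An event judged related but not primarily related. It meets the discontinuation sentence, which turns on being related, and also the extension sentence, which turns on not being primarily related.

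Two patients with the same toxicity could be handled differently depending on which sentence is followed. That bears on safety, on exposure and on the recorded reason for leaving treatment. Safety and tolerability is a secondary objective (Section 2.2). Section 13.1 requires the primary reason for discontinuation to be recorded, and Section 16.0 captures off-study documentation and toxicity attribution in the study database. No effect is claimed on the response rate, the sample size, the 5/25 decision rule or the planned adverse event tabulation.

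**Working it through.** The plan gives no figure to reproduce here. The check writes each rule as a condition on *d*, the number of consecutive days missed, for an event judged related to LY3023414, and looks for values of *d* that receive two different actions.

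**Inputs**

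- Section 11.1, permission: *d* ≤ 14.
- Section 11.1, discontinuation: *d* ≥ 14.
- Text after Table 11B, gastrointestinal toxicity: *d* ≤ 14 (two weeks).
- Text after Table 11B, organ-function toxicity: *d* ≤ 28.
- Section 13.1: *d* > 28, as a possible reason only.

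**Side by side, for a related event**

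| *d* (days) | 11.1 permission | 11.1 discontinuation | After 11B, gastrointestinal | After 11B, organ function | 13.1 |
|---|---|---|---|---|---|
| 13 or fewer | allowed | no | allowed | allowed | not met |
| 14 | allowed | discontinue | allowed | allowed | not met |
| 15 to 28 | not covered | discontinue | past limit | allowed | not met |
| 29 or more | not covered | discontinue | past limit | past limit | possible reason |

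**Overlaps**

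- Within Section 11.1: {*d* ≤ 14} and {*d* ≥ 14} share *d* = 14, which is 1 value.
- Gastrointestinal limit against the discontinuation sentence: the same single value, *d* = 14. This adds no new hold length, but a patient who uses the full allowance meets the discontinuation rule.
- Organ-function limit against the discontinuation sentence, read literally: {*d* ≤ 28} and {*d* ≥ 14} share 14, …, 28. That is 28 − 14 + 1 = 15 values, of which 14 lie beyond day 14.
- The same pair, reading 28 days as an outer ceiling subject to Section 11.1: only *d* = 14 remains, so 0 values lie beyond day 14.

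Section 13.1 first applies at *d* = 29, so it settles nothing between days 14 and 28.

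**Length of the holds in scheduled doses, at two per day**

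- 14 days: 14 × 2 = 28 doses.
- 28 days: 28 × 2 = 56 doses.
- One 21-day cycle: 21 × 2 = 42 doses.
- In cycles: 28/42 = 0.67 and 56/42 = 1.33.

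These figures show how long the holds are. They do not estimate an exposure difference caused by the wording.

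**The case against.** The strongest reply accepts the overlap at day 14 but treats it as a one-day drafting slip. The trial is single-center, the Principal Investigator can approve exceptions, and Section 11.1 describes the instructions in Tables 11A and 11B as guidelines. On days 15 to 28, a maximum is a ceiling and not an entitlement: 28 days matches the outer limit in Section 11.1, so the text after Table 11B can be read as subject to the attribution rule. The extension sentence can likewise be read as a discretionary carve-out from the discontinuation sentence. Table 11A needs no maximum of its own if Section 11.1 supplies one. The list in Section 13.1 is open-ended and separately names intolerable toxicity as a ground for withdrawal.

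Part of this stands. The ceiling reading is possible, so days 15 to 28 are a divergence on the wording and not a proven contradiction. The same applies to events related but not primarily related. The silence of Table 11A and Section 13.1 is not itself a conflict; it only means that they do not resolve the one in Section 11. Nor do the documents show that any patient would be harmed or any record would be wrong.

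The rest does not remove the problem. The word guidelines is applied to the two tables, while the 14-day sentence is separate text in mandatory terms. An exception needs a clear default to depart from, and at day 14 there is none. The ceiling reading is nowhere stated. The text after Table 11B sets different maxima for two toxicity groups, so a reader may fairly take them as toxicity-specific limits. Its required dose reduction suggests that related events are in scope, though that is an inference. Even if the organ-function rule covered only unrelated events, day 14 would still conflict.

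**Conclusion.** The concern holds. For any related event, a hold of exactly 14 days is both permitted and a mandatory reason to discontinue; this follows from the text with no further assumption. For related organ-function toxicity of Grade 2 or higher, the number of conflicting hold lengths runs from 1 (28 days as an outer ceiling under Section 11.1) to 15 (28 days as a limit in its own right), and the protocol does not say which reading applies. The mismatch between related and primarily related leaves a further group of events without a clear default.

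The documents give no frequency for holds of these lengths, so the number of patients affected is not estimated. The point is operational, with no demonstrated statistical effect. It should still be corrected, because the rules govern re-treatment after drug toxicity.

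**What to change.** Reconcile Section 11.1, the text after Table 11B and Section 13.1 so that each combination of hold length and attribution leads to one action:

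- Make the day-14 boundary non-overlapping.
- Use one relatedness term throughout and define it.
- State whether the two limits after Table 11B are subject to the Section 11.1 limit or stand apart from it, and whether they apply to related events, unrelated events or both.
- State which of these limits the Principal Investigator exception can override.
- Align the delay criterion in Section 13.1 with the result.

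Which limits to adopt is for the sponsor and investigator; no view is taken here. As a side check only, compare the 7-day hyperkalemia boundary in Table 11A with the source document, since those rows are damaged in the text available for this review and no finding is based on them.

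The cost is a clarifying amendment to Sections 11 and 13. There is no statistical cost: sample size, endpoints and analyses are unchanged.

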**Table 11A: Dose Delay Guidelines for LY3023414-Related Adverse Events**

Event Type	Grade and Frequency	Dosing
Hyperkalemia	Grade 2 (baseline potassium $\leq$ ULN)	
 
Hold until Grade <math>\leq</math>1
 
Restart at same dose if recovery to Grade <math>\leq</math>1 is <math>\leq</math>7 days.
 
Restart at next lower dose if recovery to Grade <math>\leq</math>1 is <math>\geq</math>7 days
 
Consider holding until Grade <math>\leq</math>1 taking into account change from baseline.
 
Otherwise, follow directions above
 

	Grade 2 (baseline potassium Grade 1)	
 
Hold until Grade <math>\leq</math>1
 
Restart at next lower dose
 
Discontinue
 
Discontinue
 

	Grade 3: first and second event	
 
Hold until Grade <math>\leq</math>1
 
Restart at next lower dose
 
Discontinue
 
Discontinue
 

	Grade 3: third event Grade 4	
 
Hold until Grade <math>\leq</math>1
 
Restart at next lower dose
 
Discontinue
 
Discontinue
 

Hyperglycemia	Grade 3, asymptomatic a	
 
Begin home monitoring and check at next visit; if persistent pre-dose values of Grade 3, start or adjust oral anti-hyperglycemic agent or reduce by one dose level.
 
Hold until resolution of symptoms and Grade <math>\leq</math>2.
 
Consider starting or adjusting oral anti-hyperglycemic agent or restarting at next lower dose level.
 

	Grade 3, with symptoms a	
 
Hold until resolution of symptoms and Grade <math>\leq</math>2.
 
Consider starting or adjusting oral anti-hyperglycemic agent or restarting at next lower dose level.
 

	Grade 3, with severe symptoms b , or requiring hospitalization, or Grade 4 (non-life-threatening)	
 
Hold until resolution of symptoms and Grade <math>\leq</math>2.
 
Start or adjust oral anti-hyperglycemic agent. Restart at next lower dose level.
 

	Grade 4, life-threatening	
 
Discontinue
 

Anemia	Grade 1-2	
 
Maintain dose level and initiative standard supportive care
 

	Grade 3: first event	
 
Hold until Grade <math>\leq</math>1
 
Consider restarting at next lower dose
 

	Grade 3 (second event) or Grade 4 (non-life-threatening)	
 
Hold until Grade <math>\leq</math>1
 
Restart at next lower dose
 

	Grade 4 (life threatening)	
 
Discontinue
 

Thrombocytopenia	Grade 1	
 
Maintain dose level and initiative standard supportive care
 

	Grade 2-3	
 
Hold until Grade <math>\leq 1</math>
 

	Grade 4	
 
Restart at next lower dose
 
Discontinue
 

Other Clinically Significant Drug-Related AE	Grade 1	
 
Maintain dose level and initiative standard supportive care
 

	Grade 2 (intolerable)	
 
Consider holding until Grade <math>\leq 1</math> and restarting at next lower dose
 

	Grade 3-4	
 
Hold until Grade <math>\leq 1</math>
 

	Grade 4 (life-threatening)	
 
Restart at next lower dose
 
Discontinue
 

Rash	Grade 1-2	
 
Maintain dose level and initiative standard supportive care
 

	Grade 3: First Event	
 
Hold Until <math>\leq</math> Grade 1 and restart at same dose.
 

	Grade 3: Recurrent	
 
Initiative standard supportive care and Dermatology Consultation
 
Hold Until <math>\leq</math> Grade 1 and restart at next lower dose.
 

		
 
Initiative standard supportive care and Dermatology Consultation
 

ULN = upper limit of normal. Adverse event grading is based on the current version of the National Cancer Institute Common Terminology Criteria for Adverse Events.

a Symptoms of hyperglycemia include blurry vision, polydipsia, and polyuria.

b Severe symptoms of hyperglycemia include neurological symptoms (lethargy, focal signs, or obtundation), hyperventilation, abdominal pain, and hypotension.

**Table 11B: LY3023414 Dose Reduction Schedule**

Starting Dose	200mg twice daily
Dose Level -1	150mg twice daily
Dose Level -2	100mg twice daily
Dose Level -3	Discontinue

It is expected that patients with nausea, emesis, diarrhea, or constipation will receive appropriate medical management without dose modification. However, patients with

persistent ( $\geq 24$  hours) Grade  $\geq 3$  toxicity in spite of optimal medical management require reduction of one dose level and delay in subsequent therapy for a maximum of 2 weeks until recovered to Grade 1.

Other non-hematologic toxicities with an impact on organ function of Grade  $\geq 2$  require reduction of one dose level and delay in subsequent therapy for a maximum of 28 days until recovered to Grade 1, or pre-therapy baseline

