## **9.1 TREATMENT/INTERVENTION PLAN**

### **9.2 Treatment**

LY3023414 200 mg will be dosed orally twice a day. Each cycle will be 21 days in duration. Patients will receive study treatment until disease progression, intolerable toxicity, elective withdrawal from the study, study completion, or study termination. In limited circumstances patients may be treated beyond progression if, in the opinion of the Principal Investigator, the patient is benefiting from treatment. Approval from Eli Lilly will be required in these circumstances.

LY3023414 should be taken approximately 12 hours apart. Patients should not consume food for approximately 1 hour before taking the dose of LY3023414. If a dose is vomited within one hour of ingestion, it will be replaced. If vomiting occurs more than 1 hour after dosing, it will be considered a complete dose and will not be replaced.

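### Read literally, the organ-function rule below Table 11B restarts LY3023414 at a lower dose after a drug-related life-threatening Grade 4 event for which Table 11A stops it, and nothing ranks the two rules

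*Combined protocol and SAP*

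**What the plan says.** Section 11.1 gives dosing instructions in three places.

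- **Opening text.** It describes Tables 11A and 11B as guidelines and says: "Dose modifications for LY3023414 for select AEs, should follow the guidance provided in Table 11A". Required reductions use the dose levels of Table 11B. A patient who misses 14 or more consecutive days because of drug-related events is taken off study. Delays of up to 28 days are for events not primarily due to the drug. The Principal Investigator may approve exceptions.
- **Table 11A**, which covers drug-related events. Its catch-all row, "Other Clinically Significant Drug-Related AE", holds the drug at Grade 3-4 and restarts one level lower, with a separate last line for life-threatening Grade 4.
- **Free text below Table 11B.** One sentence covers persistent gastrointestinal toxicity of Grade ≥3. The next covers "Other non-hematologic toxicities with an impact on organ function of Grade" ≥2, which "require reduction of one dose level and delay in subsequent therapy for a maximum of 28 days until recovered to Grade 1" or pre-treatment baseline.

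Table 11B steps down from 200 to 150 to 100 mg BID; the next step is discontinuation. Section 9.2 adds a general stop: "Patients will receive study treatment until disease progression, intolerable toxicity, elective withdrawal from the study, study completion, or study termination".

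**The concern.** A drug-related hepatic or renal event has no row of its own in Table 11A, so it falls under the catch-all row. It is also a non-hematologic toxicity affecting organ function, so it falls under the free text. If it is Grade 4 and life-threatening, the table stops the drug. The free text calls for a one-level reduction and a delay until recovery, which means restarting.

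What is at stake is patient safety and consistent dosing. A patient could be re-exposed after a life-threatening organ toxicity because the sentence worded as a requirement says so, while the stop sits in a table described as guidance.

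**Working it through.** The plan gives no figure to reproduce on this point. The check sets the texts side by side.

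**Step 1: what the catch-all row says at life-threatening Grade 4.** In the text extracted from the PDF this row is misaligned: the restart bullet and the discontinue bullet both appear beside the last line. Discontinue is inferred from two things:

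- Bullet order: hold and restart belong to Grade 3-4, and the final bullet belongs to the highest severity.
- Two intact rows: anemia, "Grade 4 (life threatening"), and hyperglycemia, "Grade 4, life-threatening", are each paired with discontinuation alone.

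**Step 2: where the two rules part.**

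| Organ toxicity, non-hematologic, no row of its own | Table 11A, catch-all row | Free text below Table 11B | Same action? |
|---|---|---|---|
| Related, Grade 3 or non-life-threatening Grade 4 | Hold, restart one level lower | Reduce one level, delay | Yes |
| Related, life-threatening Grade 4, on 200 mg BID | Discontinue | Restart at 150 mg BID after recovery | No |
| Related, life-threatening Grade 4, on 150 mg BID | Discontinue | Restart at 100 mg BID after recovery | No |
| Related, life-threatening Grade 4, on 100 mg BID | Discontinue | Next level is discontinuation | Yes |
| Unrelated, any grade | Does not apply | Reduce one level, delay | No conflict |

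The restart doses are 150/200 = 75% and 100/200 = 50% of the starting dose.

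**Step 3: the 14-day rule.** Every disputed case is drug-related, so the 14-day rule in the opening of section 11.1 applies. If the hold reaches 14 consecutive days, the patient is discontinued unless the Principal Investigator approves an exception. The disputed set is therefore events that recover to Grade 1 or baseline sooner, plus any exceptions.

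**Step 4: is precedence stated anywhere?**

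- The opening of section 11.1 sends selected events to Table 11A but does not mention the free text below Table 11B.
- Specificity does not decide: the table is more specific on severity, the free text on type of event.
- The stop for intolerable toxicity in sections 4.1, 4.2 and 9.2 is not defined by grade. Section 13.1 makes withdrawal for it permissive.

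**Step 5: how often.** The section on ongoing studies and clinical safety reports no related Grade 4 event among 31 phase I patients at or below the MTD. The one-sided 95% upper bound is 1 − 0.05^(1/31) = 0.092, or 9.2%. It covers all related Grade 4 events, of which the disputed ones are only a part, so it is a ceiling and not an estimate.

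**The case against.** The strongest defence is that the texts can be read together. Only Table 11A singles out life-threatening Grade 4, and its intact rows stop the drug there. Section 11.1 sends required reductions to Table 11B, so the sentence below that table can be taken to govern patients who are being reduced, not those who must stop. Three backstops support this: the 14-day rule, the intolerable-toxicity stop, and the investigator's right in section 13.1 to discontinue for any condition that may endanger the patient.

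Much of this stands. It is probably what was intended, most clinicians would stop, and the 14-day rule shrinks the disputed set. But the reading is not written down. An event that recovers within 14 days is still restarted under the required action, and the remaining stops depend on judgment.

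Three stronger inferences are not supported:

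- **That the gastrointestinal rule also contradicts the catch-all row at Grade 3.** The protocol says: "It is expected that patients with nausea, emesis, diarrhea, or constipation will receive appropriate medical management without dose modification". It then makes persistent Grade ≥3 toxicity the qualification. That is an evident exception to the table. Only its lack of an upper grade limit needs attention.
- **That the conflict is likely to arise in this trial.** The documents give no rate for life-threatening organ toxicity, so any projected probability would rest on an unsourced assumption. The Grade 4 hypophosphatemia occurred in 1 of 4 patients at 250 mg BID, above the MTD, and is not described as life-threatening or as affecting organ function.
- **That an event occurring means a patient wrongly restarted.** Clinical judgment stands between the two.

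**Conclusion.** The contradiction is real but narrow. It concerns drug-related, non-hematologic, life-threatening Grade 4 organ toxicity in patients on 200 or 150 mg BID who recover before the 14-day rule applies or receive an exception. For them one rule stops the drug and the other, taken literally, restarts it at 75% or 50% of the starting dose.

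It is probably rare, given 0 of 31 in phase I, and discretion would usually lead to stopping. The 10% versus 30% response hypotheses, the type I error, the power and the 5-of-25 criterion in section 14.1 do not depend on it.

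Confidence is medium, because the catch-all row's Discontinue is inferred from a damaged table; the original layout should be checked. The point merits correction because the error is on the unsafe side and costs little to remove.

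**What to change.** Amend section 11.1 as follows:

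1. Limit the organ-function sentence, and the persistent Grade ≥3 gastrointestinal sentence, to non-life-threatening toxicity.
2. Add: *Any LY3023414-related life-threatening Grade 4 event: discontinue, per Table 11A.*
3. Make the 28-day maximum delay in the organ-function sentence subject to the 14-day limit in the opening of section 11.1 when the event is drug-related.

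Do not give the free text general precedence over the catch-all row. That would make reduction mandatory for tolerable Grade 2 organ toxicity, whereas the table only asks the investigator to consider a hold and lower dose when Grade 2 is intolerable. It would also entrench the 28-day delay for related events.

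The cost is a short protocol amendment, with no added patients, visits or procedures.
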